Perform the UltraShape Power utilizing the U-Sculpt Power Transducer treatment according to the instruction in the User Manual.

Expected post treatment side effects are limited to Erythema (blanchable/non-blanchable), Edema, Heat sensation and pain sensation.

Post Treatment Procedures

1. Pain assessment – immediately after each treatment the subjects will be asked to rank the pain sensation during treatment using Numerical Scale Response (NSR; see Appendix III) for the UltraShape Power procedure
2. Safety aspect will be assessed before and after each treatment:
 - a. Clinical effects - All visible and palpable immediate response will be recorded for the entire treatment area using a 4-point severity scale (Table 4)
 - b. Adverse Events – Record the number, severity and type of any adverse event occurred before, through and after treatments.

Return Visits

All subjects will be requested to return to the clinic at the following time-points during the study in order to assess the clinical performance of the device:

- Visit 4: FU1 – 4 weeks (± 7 days) post last treatment.
- Visit 5: FU2 – 8 weeks (± 7 days) post last treatment.
- Visit 6: FU3 – 12 weeks (± 7 days) post last treatment.

At each return visit the following procedures will be conducted and data recorded:

- Weight.
- Ultrasound fat-thickness measurements.
- Caliper fat-thickness measurements.
- Circumference measurements.

SYNERON CANDELA Syneron Medical Ltd. Confidential	Clinical Study to Evaluate the Safety and Efficacy of the UltraShape Power Device Using the U-Sculpt Power Transducer for Abdominal Fat and Circumference Reduction			
	Protocol #	DHF21621	Rev. Date	April 05, 2016

- Skin assessment for clinical effects due the procedures:
 - Post treatment response and adverse events.
- Photographs as conducted at baseline.
- Satisfaction questionnaire performed by the investigator using the Global Aesthetic Improvement (GAI).
- Completion of the Subject Follow Up questionnaire:
 - Subjective Improvement and satisfaction performed by the subject using the Global Aesthetic Improvement (GAI).
- At the final visit a urine pregnancy test will be performed for women with bearing potential.

DATA ANALYSIS

Recording

All data will be recorded on site source documents and transcribed onto Case Report Forms (CRFs). The site will be monitored by Syneron staff or designees to assure adherence to the clinical trial requirements, subject safety, protocol procedures, and for data accuracy. The Case Report Forms and images will be reviewed and retrieved during the monitoring visit. All source documentation will remain in the subject's files at the site.

Review and Analysis of all data collected will be conducted by the Sponsor or designee as described for this protocol with the following data:

Demography and Baseline Measurements

Demographic and baseline/screening measurements (e.g., weight, height and digital images) will be collected and descriptively presented.

Treatment Visit

Skin assessment by the PI, photographs of the treated region, and pain scores will be collected used to document any adverse events to assess the device performance.

Follow-up Visit Measurements

Follow-up measurements for weight, circumference and digital images will be used for comparative measurements with their respective measurement at baseline. Primary endpoints will be evaluated 12 weeks post last treatment (Tx.3). Secondary endpoints may be evaluated at all visits.

 Syneron Medical Ltd. Confidential	Clinical Study to Evaluate the Safety and Efficacy of the UltraShape Power Device Using the U-Sculpt Power Transducer for Abdominal Fat and Circumference Reduction			
	Protocol #	DHF21621	Rev. Date	April 05, 2016

Safety

Safety of device procedure will be evaluated through skin assessments by the PI and research staff. The occurrence and severity of all complications from the start of the study will be recorded.

Protocol Revisions and/or Deviations

With the exception of emergency situations, no changes or deviations in the conduct of this protocol will be permitted without the prior approval of the sponsor.

The IRB/IEC that granted original approval for the study must be notified of all changes in the protocol, and will approve any change or deviation that may increase risk to the subject, and/or that may adversely affect the rights of the subject or validity of the investigation.

In the event of an emergency, the Investigator will institute any medical procedures deemed appropriate. However, all such procedures must be promptly reported to the sponsor and the IRB/IEC.

ADVERSE EVENTS (AE)

An adverse event (AE) is any adverse change in health or side effect that occurs in a study participant during their participation in the study.

Anticipated Adverse Effects

Following treatment with the UltraShape Power the following local adverse effects could occur (anticipated):

- Purpura
- Blister
- Bruising
- Bullae
- Erosion
- soreness
- First degree burn
- Second degree burn

An adverse event (AE) is any undesired clinical occurrence in a study subject as indicated by signs, symptoms, illnesses, events that develop or worsen in severity in association with the study when deemed by the Investigator to be related to use of the device or study procedures. The Investigator will document all adverse signs and symptoms regardless of severity or frequency that are either volunteered by subjects or observed during the course of the study that are related to the device. The Investigator will also record adverse experiences of subjects resulting from concurrent illnesses, reactions to concurrent medications, or progression of disease states that the Investigator deems related to the device. Included in the description will be the nature of the sign or symptom, the date of onset, whether the event was serious, the severity, the relationship to study procedures or investigational device, the action taken, the

 Syneron Medical Ltd. Confidential	Clinical Study to Evaluate the Safety and Efficacy of the UltraShape Power Device Using the U-Sculpt Power Transducer for Abdominal Fat and Circumference Reduction			
	Protocol #	DHF21621	Rev. Date	April 05, 2016

date of resolution, and the outcome. The Principal Investigator will determine the relationship of the adverse device effect to the investigational device.

Unanticipated Adverse Device Effects

For device studies, part 21 CFR 812.3(s) uses the term unanticipated adverse device effect which is defined as any serious adverse effect on health or safety or any life-threatening problem or death caused by, or associated with the device, if that effect, problem, or death was not previously identified in nature, severity, or degree of incidence in the investigational plan or application (including a supplementary plan or application), or any other unanticipated serious problem associated with a device that relates to the rights, safety, or welfare of subjects.

Significant device failure may constitute an adverse event if an undesirable experience occurs. This definition includes any event resulting from insufficiencies or inadequacies in the instructions for use or the deployment of the device, or any event that is a result of a user error.

All unanticipated adverse effects will be graded as follows:

Mild: Sign or symptom, usually transient, non-life-threatening requiring no special treatment and generally not interfering with usual activities.

Moderate: Sign or symptom, non-life-threatening which may be ameliorated by simple therapeutic measures, and may interfere with usual activity.

Major: Sign or symptom that is intense or debilitating but non-life-threatening and that interferes with usual activities. Recovery is usually aided by therapeutic measures and the discontinuation of the study device may be required.

Severe: Any untoward medical occurrence that at any time results in death or life-threatening illness, resulting in persistent or significant disability/incapacity.

The relationship of the adverse effect to the study is defined as follows:

Probable: An adverse event has a strong temporal relationship to study device, and another etiology is unlikely or significantly less likely.

Possible: An adverse event has a strong temporal relationship to the study device, and an alternative etiology is equally or less likely compared to the potential relationship to study device.

Probably not: An adverse event has little or no temporal relationship to the study device and/or a more likely alternative etiology exists.

Not related: An adverse event has no temporal relationship to study device or has a much more likely alternative etiology.

 Syneron Medical Ltd. Confidential	Clinical Study to Evaluate the Safety and Efficacy of the UltraShape Power Device Using the U-Sculpt Power Transducer for Abdominal Fat and Circumference Reduction			
	Protocol #	DHF21621	Rev. Date	April 05, 2016

Reporting Adverse Events (AE) and Serious Adverse Events (SAE)

Anticipated Adverse Events: Anticipated adverse events in this study include Purpura, blistering, bruising, bullae, erosion, soreness and burn. If an unanticipated adverse event occurs at any time during or after the use of the UltraShape Power device, the Investigator must report it to Syneron.

The Investigator must report all unanticipated adverse device effects that are serious in nature to the clinical study monitor immediately or within twenty-four hours by telephone (see below). If such an unanticipated adverse device effect is reported after normal working hours, the Investigator will leave a voice message at the monitor’s telephone number with accompanying report of the unanticipated adverse device effect faxed or sent to the fax number/e-mail address below:

[name], Global VP of Clinical Affairs
Telephone/Fax No.: From the U.S. [name]
[name] (cell)
E-mail: [contact]

A written report prepared by the Principal Investigator must follow within five working days to both the IRB and to Syneron and should include a full description of the event and sequence.

Measures taken to protect the rights and welfare of subject

Research records will be available to study personnel, the sponsor, Ethics Review Committee and regulatory agencies as required. Research records may be used for purposes of medical education, after removal of subject names or other identifying information. In the ICF the subjects will be informed that the photographs and video taken of them during the study may be made available to the sponsor for marketing and instructional purposes, after removal of identifying information. All images collected will be stored without personal subject identifiers at the site and at Syneron.

RISK/BENEFIT ANALYSIS

Risks

Syneron has determined that the *UltraShape Power* system is non-significant risk device. As indicated in the AE section, the anticipated risks associated with the use of both of the systems are:

- Purpura
- Blister
- Bruising
- Erosion
- soreness
- First degree burn

 Syneron Medical Ltd. Confidential	Clinical Study to Evaluate the Safety and Efficacy of the UltraShape Power Device Using the U-Sculpt Power Transducer for Abdominal Fat and Circumference Reduction			
	Protocol #	DHF21621	Rev. Date	April 05, 2016

- Bullae
- Second degree burn

Over 1000 subjects worldwide participated in clinical research and underwent treatment with the different *UltraShape* devices. The *UltraShape Power* device will be used in this study was previously used in studies and emitted the same acoustic energy. To date, no serious adverse events or unanticipated AEs have been reported. The reported AEs relate to skin and subcutaneous tissue, confined to the treatment area and were all mild in nature and resolved within the study period.

Potential benefits to participating individuals and to society

Subjects may or may not benefit from reduction of subcutaneous fatty tissue on the treated area via a non-invasive technique resulting in body contouring improvement. All subjects in the treatment groups are expected to have some benefit from the treatment procedures as would be expected for the commercial devices (*UltraShape Power*). Subject will receive all treatment procedures at no cost. This study will benefit the advancement of medicine by generating data on safety and efficacy that will aid in the development of an alternative treatment options to procedures with higher potential risks subjects, such as liposuction. The results of this study will help to determine whether this device is safe and effective for improvement of localized subcutaneous fat.

Conclusion:

In light of the potential benefits of non-invasive body contouring relative to its risks, the potential benefits associated with the use of the *UltraShape Power System* outweigh its risks, supporting study initiation.

ETHICS AND GOOD CLINICAL PRACTICE

This study will be carried out in compliance with the following:

- Syneron Standard Operating Procedures.
- Declaration of Helsinki, concerning medical research in humans (Recommendations Guiding Physicians in Biomedical Research Involving Human Subjects, Helsinki 1964, amended Tokyo, 1975, Venice 1983, and Hong Kong 1989).
- US Code of Federal Regulations (Title 21CFR including parts 50, 56 and 812 governing informed consent and IRB regulations).
- International Conference on Harmonization (ICH) Harmonized Tripartite Guideline for Good Clinical Practice (GCP), 1996.

 Syneron Medical Ltd. Confidential	Clinical Study to Evaluate the Safety and Efficacy of the UltraShape Power Device Using the U-Sculpt Power Transducer for Abdominal Fat and Circumference Reduction			
	Protocol #	DHF21621	Rev. Date	April 05, 2016

QUALITY ASSURANCE AND STUDY MONITORING

Study Monitoring/Auditing/Inspection

The Study Monitor will be responsible for monitoring the study sites to review the data being collected. The sponsor shall implement and maintain quality control and quality assurance procedures with written standard operating procedures (SOPs) to ensure that the trial is being conducted and data are generated, documented and reported in compliance with the protocol, Good Clinical Practice (GCP) and applicable regulatory requirements. Visits will be made prior to the initiation of the study, at scheduled intervals throughout the study, and at termination of the study.

Once enrollment and treatments have begun, monitoring visits will take place more frequently pending enrollment and study activities.

The sponsor and site will maintain regular phone and e-mail correspondence throughout the study to confirm compliance of study procedures.

The investigator/institution agrees to allow the monitor and other authorized personnel direct access to source data/ documents for trial related monitoring, the clinical supplies storage/dispensing area and to provide all documents in the Investigator Regulatory Binder for review, and to assist site auditors in their activities if requested. Requests by the Health Canada or regulatory agencies of other countries to inspect the study site may be made after adequate notification. The investigator may be required to assist the regulatory inspectors in their duties, if requested.

ADMINISTRATIVE PROCEDURES

Supply and Disposition of Study Device

The *UltraShape Power* device and Parker Gel (coupler agents) will be supplied to the participating clinic. The device will be maintained by the Sponsor, as needed. Unused equipment or coupler agents will be returned to the sponsor at the end of the study. At the end of all planned treatment sessions the devices will be returned to Syneron.

Control & Disposition of the Investigational Device

The *UltraShape Power* device will be used according to the instructions of the Sponsor and manufacturer, Syneron Medical. At the end of this study, any materials provided specifically for use in this study may be returned to the Sponsor, as described in the Clinical Trial Agreement and study budget.

 Syneron Medical Ltd. Confidential	Clinical Study to Evaluate the Safety and Efficacy of the UltraShape Power Device Using the U-Sculpt Power Transducer for Abdominal Fat and Circumference Reduction			
	Protocol #	DHF21621	Rev. Date	April 05, 2016

Informed Consent

The Study Personnel will obtain written Informed Consent prior to the subject’s participation in any study procedures. The Study Personnel will inform the subjects of the experimental procedure to be utilized and assure the subjects that their decision regarding participation in the study will have no bearing on the quality of medical care received and that their decision whether to participate in the study is strictly voluntary.

During the initial interview, the subject will be assured that they are free to change their mind and will be allowed to participate in the study or withdraw from the study with no adverse effect on their standard medical care.

Monitoring Plan

At least 3 monitoring visits are projected during the whole study. The frequency of which will be based on enrolment, study activities and the study visit scheduled. The first visit is scheduled at the initiation of the study prior to the first subject treatment in the study. The second visit is scheduled after enrolment and treatment has been initiated and a third visit will be for a close-out visit for the study. Interim visits may be conducted as needed to assure compliance to the study protocol and regulatory requirements. The number and frequency of monitoring visits may also be increased per the sponsor decision to collect data and images post treatment.

Case Report Forms

Paper case report forms will be used in this trial. All protocol-required information collected during the study must be entered in the appropriate field of the case report form (CRF). The investigator, or designated representative, should complete the appropriate CRF fields as soon as possible after information is collected. The information must match the information that exists as source documents in the clinic chart, hospital chart, and/or investigator’s files. An explanation should be given for all missing data.

It is the investigator’s responsibility to assure the accurate completion, review, and approval of all CRFs and the timely completion and submission of all adverse event forms.

Record Maintenance

The investigator shall retain a copy of all study documents in accordance with the FDA regulations which specify that records should be kept for a period of two years: 1) following the date a marketing application either is approved or disapproved for the use, or 2) following notification to FDA that no application is being filed and/or that the study has been discontinued.

 Syneron Medical Ltd. Confidential	Clinical Study to Evaluate the Safety and Efficacy of the UltraShape Power Device Using the U-Sculpt Power Transducer for Abdominal Fat and Circumference Reduction			
	Protocol #	DHF21621	Rev. Date	April 05, 2016

If an investigator leaves the study site before record retention obligations have expired, the sponsor should be notified in writing of the person designated to retain the study documents during and after the study.

Handling of clinical data. The data are entered into a secure database that only the sponsor has access to. Admission to the database requires access to a password-protected network secured by the Sponsor. This database is maintained by Syneron that performs backups, data verification, and application upgrades. All equipment housing the clinical data is located in locked rooms or a secure computer network. The only individuals, who view, extract and analyze data for protocol reports and publications are physicians and nurses who are members of the study team or Sponsors. Only authorized personnel of the Sponsors have access to databases.

Any paper copies of subject medical records or research records are stored in secure cabinets at the study site.

PUBLICATION POLICY

The investigator will not publish the study results and will not disclose confidential information received from Syneron without prior written agreement from Syneron. Such confidential information shall include any and all information relating to this study as described in the Clinical Trial Agreement. In the event that Syneron consents to the publication of data from this study, the investigator will provide Syneron manuscripts for review thirty days before submission for publication. Syneron will have no editorial rights over manuscripts. The investigator will also provide Syneron with advance notice of at least (30) days, of any presentation, lecture, abstract session, etc., in which any results from the study will be disclosed.

 Syneron Medical Ltd. Confidential	Clinical Study to Evaluate the Safety and Efficacy of the UltraShape Power Device Using the U-Sculpt Power Transducer for Abdominal Fat and Circumference Reduction			
	Protocol #	DHF21621	Rev. Date	April 05, 2016

BIBLIOGRAPHY

1. Arner P. *OBESITY AND THE ADIPOCYTE, Regional adiposity in man*. Journal of Endocrinology (1997) 155, 191–192
2. Illouz YG, de Villiers YT. *Body Sculpturing by Lipoplasty*. Edinburgh: Churchill Livingstone, 1989.

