 Syneron Medical Ltd. Confidential	Clinical Study to Evaluate the Safety and Efficacy of the UltraShape Power Device Using the U-Sculpt Power Transducer for Abdominal Fat and Circumference Reduction			
	Protocol #	DHF21621	Rev. Date	April 05, 2016

	7. Subject improvement and satisfaction: Improvement and satisfaction assessment will be performed independently by the subject himself using a pre-defined scale questionnaire. The subjects will answer this questionnaire at each follow-up visit (4wk FU, 8wk FU and 12wk FU)
Efficacy Endpoints	Primary and secondary objectives will be measured using the next efficacy endpoints: 
 1. Fat thickness measurements using Ultrasound device 2. Fat thickness measurements using calibrated Caliper 3. Circumference measurements of the abdominal area using Measuring Tape 4. Investigator satisfaction using a pre-defined scale 5. Subject improvement and satisfaction using a pre-defined scale 6. Photography
Safety Endpoints	
 1. The number, severity and type of any adverse event recorded throughout the study and post treatment (immediate and delayed response) 2. Pain assessment using NSR scale
Statistical Methods	Descriptive statistics will be used to present changes in the assessments along the study course. Circumference measurements and subject assessments' and satisfaction data will be analyzed using two-tailed Wilcoxon Signed Rank test and/or paired t-test (alpha=0.05) to analyze the data difference from baseline and longitudinal change.

INTRODUCTION AND RATIONALE

Background

Adipose tissue is a loose type of connective tissue specialized to store lipids. The majority of lipids stored in adipose cells are triglycerides formed from imported free fatty acids and glycerol. It is not uniformly distributed in the body. The major adipose depot is subcutaneous (about 80% of all body fat).¹ In men it normally represents 15-20% of body weight and in women, 20-25% of body weight. A certain amount of body fat is necessary for normal female reproduction and health. Subcutaneous adipose tissue helps to shape, cushion and insulate the body and provides padding to some organs.

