1. Statistically significant abdominal fat reduction post UltraShape Power treatments as measured by Ultrasound device at Pre Tx.3, 4 weeks, and 8 weeks follow-up (4wk FU and 8wk FU) versus baseline.
2. Statistically significant abdominal fat reduction post UltraShape Power treatments as measured by calibrated Caliper at Pre Tx.2, Pre Tx.3, 4 weeks, 8 weeks and 12 weeks follow-up (4wk FU, 8wk FU and 12wk FU) versus baseline.
3. Statistically significant abdominal circumference reduction post UltraShape Power treatment/s at Pre Tx.2, Pre Tx.3, 4 weeks, 8 weeks and 12 weeks follow-up (4wk FU, 8wk FU and 12wk FU) versus baseline.
4. Investigator satisfaction:
Satisfaction assessment will be performed by the study investigator using a pre-defined scale questionnaire. The investigator will answer this questionnaire at each follow-up visit (4wk FU, 8wk FU and 12wk FU).
5. Subject improvement and satisfaction:
Improvement and satisfaction assessment will be performed independently by the subject himself using a pre-defined scale questionnaire. The subjects will answer this questionnaire at each follow-up visit (4wk FU, 8wk FU and 12wk FU).

Primary and Secondary Efficacy Endpoint

Primary and secondary objectives will be measured using the next efficacy endpoints:

1. Fat thickness measurements using Ultrasound device
2. Fat thickness measurements using calibrated Caliper
3. Circumference measurements of the abdominal area using Measuring Tape
4. Investigator satisfaction using a pre-defined scale
5. Subject improvement and satisfaction using a pre-defined scale
6. Photography

 Syneron Medical Ltd. Confidential	Clinical Study to Evaluate the Safety and Efficacy of the UltraShape Power Device Using the U-Sculpt Power Transducer for Abdominal Fat and Circumference Reduction			
	Protocol #	DHF21621	Rev. Date	April 05, 2016

Primary Safety Endpoint

The number, severity and type of any adverse event recorded throughout the study and post treatment (discomfort (pain), immediate and delayed response).

1. Occurrence of expected post treatment immediate response including erythema and edema and during all study period based on predefined scale (Table 4).
2. Number, severity and type of any adverse event recorded throughout the course of the study.

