Treatment-associated pain	Immediately after each treatment (Tx.1, Tx.2 & Tx.3)	Subject will be asked to rank/ assess pain level during treatment based on the Numerical Scale Response (NSR scale) - Appendix III Appendix III - Pain assessment
Immediate response assessment	Immediately after each treatment (Tx.1, Tx.2 & Tx.3)	Post Treatment Side Effect Severity Scale (Table 4)
Investigator satisfaction	At all follow-up visits (4wk FU, 8wk FU and 12wk FU)	Satisfaction Questionnaire (Table 6)
Subject satisfaction		Satisfaction Questionnaire (Table 6)
Improvement assessment		Improvement Questionnaire (Table 5)
Safety	During treatment and throughout study.	Examination of skin in the treated area, interview subjects, Adverse Events form, Occurrence and Severity Ratings, as well as relation to treatment, action taken and outcome

[figure not shown]

Figure 2: Study Flow-Chart (Visits at the Clinic)

SYNERON CANDELA Syneron Medical Ltd. Confidential	Clinical Study to Evaluate the Safety and Efficacy of the UltraShape Power Device Using the U-Sculpt Power Transducer for Abdominal Fat and Circumference Reduction			
	Protocol #	DHF21621	Rev. Date	April 05, 2016

Pre-Treatment Procedures

Screening and Baseline procedures may be conducted on the same visit day as the treatment, prior to the treatment. It is expected that the screening and baseline procedures will be conducted during the same visit and the treatment visit procedures will take up to 2 hours.

Screening

1. ICF - Prior to any study procedures, informed consent will be obtained. When the subject fully understands the possible benefits and risks of the study, the subject will be asked to sign and date the informed consent form (ICF). The subject will be given a copy of the signed ICF.
2. Subject ID - subjects will be assigned a study subject ID number.
3. Medical History - A medical history will be obtained to determine if the subject meets the study criteria, including a list of all prescribed and over the counter medications taken within the previous 6 months will be recorded.
4. Skin Exam - The subject will undergo a routine skin exam to determine if they meet the study criteria including the presence of fatty tissue deposits in the treatment area.
5. BMI – the volunteers’ height and weight will be taken for calculation of BMI.

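### As worded, the synopsis tests subject satisfaction and improvement for a difference from baseline, but neither rating is collected at baseline

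*Combined protocol and SAP*

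**What the plan says.** The only inferential plan for the questionnaires is the Statistical Methods row of Table 1 (Study Synopsis). It takes circumference and the subjects' assessment and satisfaction data together and says they "will be analyzed using two-tailed Wilcoxon Signed Rank test and/or paired t-test (alpha=0.05) to analyze the data difference from baseline and longitudinal change". The same row also plans descriptive statistics.

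On timing, item 5 of Secondary Objectives (subject improvement and satisfaction) says: "The subjects will answer this questionnaire at each follow-up visit (4wk FU, 8wk FU and 12wk FU"). Table 2 gives the timing as "At all follow-up visits (4wk FU, 8wk FU and 12wk FU"). That cell stands on the investigator satisfaction row and appears to be merged over the two subject rows below it. Appendix I, Table 3 has three marks on the Subject Questionnaire row, which fits those visits. The Baseline procedures list no questionnaire.

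On instruments, Table 2 assigns improvement to the "Improvement Questionnaire (Table 5") and both satisfaction ratings to the "Satisfaction Questionnaire (Table 6"). The Return Visits section differs: "Satisfaction questionnaire performed by the investigator using the Global Aesthetic Improvement (GAI"). It also puts the subject's improvement and satisfaction on the GAI.

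In Appendix II, Table 5 (GAI) runs from 0, no change, to 3, significant improvement. Table 6 runs from 0, dissatisfied, through 1, no opinion, to 3, very satisfied.

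**The concern.** A paired test of difference from baseline needs a baseline score for each subject. None is scheduled for satisfaction or improvement, so one stated analysis of a secondary endpoint cannot be carried out as written. An analyst would have to invent a reference value after the fact.

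For satisfaction there is no natural reference. Testing against the neutral category would be a test against a chosen constant, which the plan does not state. For improvement, 0 is a natural reference, but a scale with no category below 0 makes a nominally two-tailed test one-directional. A small p-value from such a test could be reported as efficacy evidence although very few subjects had noticed any change.

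**Working it through.** **Step 1. Does each measure named in the sentence have a baseline?**

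| Measure | Collected at | Baseline difference |
|---|---|---|
| Circumference | Before each treatment and at all follow-ups (Table 2) | Defined |
| Subject satisfaction, Table 6 | 4, 8 and 12 weeks | Undefined |
| Subject improvement, Table 5 | 4, 8 and 12 weeks | No baseline score; the rating is itself a change |

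Change between 4, 8 and 12 weeks can be computed for all three.

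**Step 2. Does the rest of the plan call for a baseline test of the ratings?** In Secondary Objectives, the circumference item is framed as a significance claim against baseline ("Statistically significant abdominal circumference reduction post UltraShape Power treatment/s at Pre Tx.2, Pre Tx.3" and later visits), as are the ultrasound and caliper items. The two questionnaire items carry no such criterion. The Follow-up Visit Measurements section says "Follow-up measurements for weight, circumference and digital images will be used for comparative measurements with their respective measurement at baseline" and does not mention questionnaires. It also omits ultrasound and caliper, so its silence is weak evidence.

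**Step 3. What would a test of the GAI against 0 do?** The plan does not propose this test; it is the only form that a baseline test of the GAI could take. The plan gives no expected response rate and no sample-size calculation, so there is no planned figure to reproduce, and what follows is a hypothetical illustration. Inputs: n = 120 (the plan's upper limit), n = 60 (an assumed lower case), alpha 0.05 two-sided, and k subjects rating above 0.

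- *Exact signed-rank test.* Zeros drop out and all k remaining signs are positive, so p = 2 × 0.5^k, whatever n and whatever the size of the answers. For k = 5, p = 2 × 0.03125 = 0.0625. For k = 6, p = 2 × 0.015625 = 0.031. Six is the smallest k below 0.05.
- *What six means.* At n = 120, 6/120 = 5.0% (exact 95% CI 1.9% to 10.6%), with the other 95% reporting no change. At n = 60, 6/60 = 10.0% (3.8% to 20.5%).
- *Paired t-test, k answers of 1 and the rest 0.* t = √[k(n − 1)/(n − k)]. For n = 120 and k = 4, t = √(4 × 119/116) = 2.026, p = 0.045; the exact signed-rank p for k = 4 is 0.125. For k = 12, t = √(12 × 119/108) = 3.636, p = 0.0004, against 0.0005. The open choice of test therefore matters only near the threshold.
- *Direction.* No difference can be negative, so the test cannot reject against the device.

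**Step 4. What would a descriptive estimate give?** If 70% were satisfied (an assumed figure), the exact 95% CI would be 61.0% to 78.0% for 84/120 and 56.8% to 81.2% for 42/60.

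**The case against.** The strongest reply is that the sentence is loose synopsis wording that joins two kinds of data to two purposes. It can be read distributively: baseline difference for circumference, longitudinal change for the ratings. The wording of Secondary Objectives fits that reading. This stands as a possible intention. It does not remove the point, because the sentence does not make the split and no other section states a test for these ratings.

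The test against 0 is inferred, and six improved subjects in 120 is a boundary case that nothing in the plan predicts; the section on potential benefits expects some benefit in all treated subjects. That also stands. The figures show how the test behaves and do not correct any planned number.

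A figure after Table 5 is not shown in the text available, so the original form might include a category for worsening. The one-direction statement depends on Table 5 being complete as it reads. The missing baseline does not.

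A reader might infer that no subject-completed questionnaire is collected before the follow-up period. The documents do not support that: the NSR comfort rating is also called a questionnaire and is answered after each of the three treatments. A reader might also infer that the questionnaires cannot be tested at all, or that the main efficacy claim is weakened. Neither follows, because comparisons between follow-up visits remain possible and the primary ultrasound endpoint does not use these ratings.

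**Conclusion.** The point holds for the sentence as written. A difference from baseline is undefined for subject satisfaction. For improvement it reduces to a test against 0, which could reject only in favour of the device if Table 5 is complete as it reads. At n = 120, six subjects with any improvement would be enough for an exact p of 0.031.

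The size is small: a minor correction to a secondary endpoint. Circumference, fat thickness, between-visit comparisons of the ratings and the descriptive statistics are unaffected. The structural part rests only on the visit schedule and needs no assumption about response rates. Whether satisfaction is rated on Table 6 or on the GAI is a linked inconsistency. It has to be settled as well, because the instrument decides whether any test against 0 could exist for satisfaction.

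**What to change.** 1. In the Statistical Methods row of Table 1, limit difference from baseline to measures that have a baseline value.
2. For subject satisfaction and improvement, report the full category distribution at 4, 8 and 12 weeks. Add the proportion with GAI 1 or higher and the proportion satisfied or very satisfied, each with an exact 95% confidence interval. The GAI proportion still cannot show worsening, so it should be read alongside the full distribution.
3. Limit paired tests on these two ratings to change between follow-up visits. Leave the NSR comfort ratings after Tx.1 to Tx.3 outside this restriction.
4. Reconcile Table 2 (satisfaction on Table 6) with Return Visits (satisfaction on the GAI), so that one instrument is named for each endpoint and rater.

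**Cost.** One sentence in the synopsis and aligned wording in Table 2 and Return Visits, with the IRB/IEC notification that the protocol requires for any change. There would be no p-value versus baseline for these ratings. If the sites' forms already carry Table 6, no new data are needed. If they carry only the GAI, naming Table 6 would need a change to the paper case report form at up to 10 sites, and satisfaction answers already collected on the GAI could not be converted.
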